4.1.3. Eye Drop Sub-Study

4.1.3.1. Sub-Study Schema

4.1.3.2. Sub-Study Design

Up to 60 participants from Cohorts A to G may voluntarily consent to join a sub-study to evaluate the effect of different prophylactic eye drops, beyond standard lubricating eye drops. Consenting participants will be assigned to cohorts of 10 to 20 participants who will receive additional eye drops as primary prophylaxis to mitigate ocular symptoms and signs. Participants in this sub-study will be monitored for the frequency and severity of ocular events and will have an ocular examination after 2 cycles of therapy regardless of whether they have ocular symptoms and signs, as required of all participants in this trial. Major differences in ocular AEs (eg, 50% reduction in participants with ≥ Grade 2 keratopathy, or 50% reduction in ocular AEs leading to dose reduction/discontinuation) will be used to determine whether different eye drop regimens provide benefit in comparison to others and to participants on trial that only receive prophylactic lubricating drops. Knowledge gained from this sub-study may be applied to the remainder of the study participants. Details of the eye drop options are described in Section 7.2.1.

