7.2.1. Eye Drop Options

During this study, different eye drops will be tested to mitigate ocular events. Investigators and participants will be informed of which eye drop regimen(s) they should use before the start of study treatment. Participants are required to receive prophylactic lubricating artificial tears and may receive additional eye drop(s) as prophylaxis as recommended by the investigators and Sponsor.

A formal voluntary ocular sub-study may be used to assign participants to different eye drop regimens to compare the frequency and severity of ocular AEs (Section 4.1.3).

Lubricating Artificial Tears

All participants should be instructed to use lubricating artificial tears for the treatment and prophylaxis of ocular symptoms and signs, as directed by the product label or the treating physician. Participants should start their regimen of lubricating artificial tears prior to each dose of IMGC936 and after dosing continue application at least 4 times per day. Lubricating artificial tears are to be continued indefinitely throughout study treatment, at the ophthalmologist or treating physician's discretion.

Vasoconstricting Eye Drops

If instructed to do so, participants should also use refrigerated, topical vasoconstricting eye drops (ie, prescription strength brimonidine 0.1-0.2% twice daily, or potent adrenergic receptor agonist) unless the risks outweigh the benefits as determined by the treating physician or ophthalmologist (see product label warnings and drug interactions). Vasoconstricting eye drops should be applied within 1 hour prior to dosing of IMGC936 and continued for at least 3 days or throughout study treatment at a frequency as directed by the product label, and at the local ophthalmologist or treating physician discretion. If ocular symptoms occur that may be caused by vasoconstricting eye drops (eg, conjunctivitis, redness, itching, burning, visual disturbance), they may be interrupted or discontinued at the discretion of the local ophthalmologist or treating physician.

Corticosteroid Eye Drops

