If instructed to do so, participants should also use prophylactic corticosteroid eye drops and should be instructed to self-administer 1% prednisolone (Pred Forte or equivalent). For Schedule A participants, steroid should be self-administered 6 times daily on the day of dosing through Day 4, and 4 times daily on Day 5 to Day 8 of each cycle during the study. For Schedule B participants, steroid should be self-administered 6 times daily on the day of dosing through 4 days after each dose.

Participants receiving multiple drops should be advised to administer the drops at different times if feasible. Participants are suggested to wait at least 15 to 30 minutes between the administration of different eye drops.

In addition, local ophthalmologists or treating physicians may choose to begin therapeutic corticosteroid eye drops when ocular symptoms or signs occur. These may be used in addition to the prophylactic regimen used.

Cyclosporine Eye Drops

If instructed to do so, participants should also use refrigerated, topical cyclosporine (0.025% - 0.2%) eye drops unless the risks outweigh the benefits as determined by the treating physician or ophthalmologist. Cyclosporine eye drops should be applied within 1 hour prior to dosing of IMGC936 and continued for at least 3 days or throughout study treatment at a frequency as directed by the product label, and at the local ophthalmologist or treating physician discretion unless contraindicated. If ocular symptoms occur that may be caused by cyclosporine eye drops (eg, itching, burning, swelling), they may be interrupted or discontinued at the discretion of the local ophthalmologist or treating physician.

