## 7.2. Adverse Events (AEs)

AEs will be documented on the AE eCRF and monitored continuously throughout the study from the time of informed consent until 30 days after the patient's last study drug or until the event has resolved, stabilized, or returned to baseline. AEs attributed to study procedures, including those events that occur prior to the first dose, should also be documented on the AE eCRF.

AE data are available to ImmunoGen from 2 sources, the eCRFs and the serious adverse event (SAE) forms. While reconciliation will be performed, the production of data summaries and listings will be based on the data collected on the eCRF.

Pre-treatment AEs are defined as AEs with an onset date prior to the first dose of study drug. TEAEs are defined as AEs with an onset date on or after the first dose of study drug, and within 30 days of the last dose of study drug or prior to the start of a new anti-cancer treatment, whichever occurs first. Medical history conditions that exist before the initiation of study drug but worsen in severity during the study will also be recorded on the AE eCRF as an AE and will be included as treatment-emergent in the summary tables and listings.

The adverse events will be coded using MedDRA, associating lower-level terms with PT and SOC by the primary hierarchy. The tables will display the counts and percentages of patients who reported at least 1 TEAE in each SOC represented in the AE data. Within each SOC, the tables will display the counts and percentages of patients reporting at least 1 TEAE as designated by the PT.

AEs are graded using Common Terminology Criteria for Adverse Events (CTCAE) Version 5.0. AE summaries may include summaries for all AEs and by the maximum CTCAE grade for the item being summarized (ie, SOC or PT). In these cases, the outputs will include a row for All Grades as well as rows for the 5 potential CTCAE grades, Grade 1 (Mild), Grade 2 (Moderate), Grade 3 (Severe), Grade 4 (Life threatening or disabling), or Grade 5 (Death). AEs missing a severity grade will not be included in the Grade 1-5 rows of the tables. An AE reported by a patient more than once will be represented in the most severe category.

Ocular AEs including blurred vision events and grouped keratopathy events will be analyzed for outcome, resolution, time to onset and time to resolution. Patients at 6mg/kg who administered different prophylactic eye drops will be further analyzed.

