The criteria for eye drop subgroups are defined as follows.

Brimonidine + lubricating eye drop group: patient who started brimonidine prior to or on C1D1 reported in concomitant medicine or cycle 1 eye drop compliance form.

Steroid + lubricating eye drop group: patient who started steroid prior to or on C1D1 reported in concomitant medicine or cycle 1 eye drop compliance form.

Lubricating only eye drop group: all other patients at 6 mg/kg who are not included in above two groups.

The following AE summary tables will be produced:

- An overall summary: present the numbers (and percentages) of patients with any TEAEs, TEAEs ≥ Grade 3, study drug related AEs, AEs leading to permanent discontinuation of study drug, TEAEs leading to death, and any death during the study treatment or within 30 days of last dose.
- All TEAEs
- TEAEs with CTCAE severity Grade  $\geq 3$
- Study drug related TEAEs (ie, TEAEs with a drug relationship of possibly related, probably related, or definitely related; TEAEs with missing drug relationships will be also included).
- Study drug related TEAEs with CTCAE severity Grade  $\geq 3$
- Serious TEAEs
- Non-Serious TEAEs (ie, TEAEs excluding SAEs)

Confidential and Proprietary ImmunoGen, Inc.

- Study drug related SAEs
- TEAEs leading to discontinuation of study drug (ie, TEAEs with an action taken of study drug discontinued permanently)
- TEAEs leading to interruption of study drug (ie, TEAEs with an action taken of study drug with dose interrupted)
- Study drug related TEAEs leading to discontinuation of study drug
- Study drug related TEAEs leading to interruption of study drug
- TEAEs leading to death (ie, TEAEs with CTCAE Grade 5)
- Deaths on study treatment or within 30 days of the last dose. This table includes all deaths during study treatment or within 30 days of the last dose, regardless of cause of death.
- Ocular TEAE resolution (blurred vision and keratopathy)
- Time to onset of first ocular TEAE (blurred and keratopathy)

Time to resolution of ocular TEAE (blurred vision and keratopathy)The following listings will be produced:

- All pre-treatment AEs
- All TEAEs, sorted chronologically within patient. This listing includes SOC, PT, onset and end dates, and other relevant information.
- Serious TEAEs, sorted chronologically within patient
- TEAEs leading to discontinuation of study drug
- TEAEs leading to interruption of study drug
- Study drug related TEAEs
- Study drug related SAEs
- Dose-limiting toxicities (DLTs)

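### The eye-drop groups in SAP 7.2 are not mutually exclusive, and the lubricating-only group is not limited to patients on lubricating drops alone

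*SAP*

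**What the plan says.** Exploring ocular primary prophylaxis is an exploratory objective of the expansion phase (Protocol 3.2.3, SAP 2.2.3).

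**Protocol.** Section 7.2.1 requires lubricating artificial tears for everyone and describes three additional options:

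- Vasoconstricting drops, described as "prescription strength brimonidine 0.1-0.2% twice daily, or potent adrenergic receptor agonist".
- Corticosteroid drops.
- Cyclosporine: "If instructed to do so, participants should also use refrigerated, topical cyclosporine (0.025% - 0.2%) eye drops".

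Section 4.1.3.2 compares regimens with one another and with "participants on trial that only receive prophylactic lubricating drops". It gives a 50% reduction in certain ocular events as an example of a major difference, and says that what is learned may be applied to the remaining participants.

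**SAP.** Section 7.2 states: "Patients at 6mg/kg who administered different prophylactic eye drops will be further analyzed". It then defines three groups:

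- Brimonidine plus lubricating: "patient who started brimonidine prior to or on C1D1 reported in concomitant medicine or cycle 1 eye drop compliance form".
- Steroid plus lubricating: "patient who started steroid prior to or on C1D1 reported in concomitant medicine or cycle 1 eye drop compliance form".
- The remainder: "Lubricating only eye drop group: all other patients at 6 mg/kg who are not included in above two groups".

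There is no group for cyclosporine, for another adrenergic agonist or for combinations, and no order of precedence. SAP 4.9 and 4.10 plan no hypothesis test.

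**The concern.** The third group is defined by exclusion from the first two, not by what its patients used. Its label claims lubricating drops only, but nothing in the rule checks this. The two active definitions do not exclude each other either, so two programmers could handle the same patient differently.

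Because no test is planned, the descriptive results by group are all the evidence that this objective will produce. If the groups do not mean what their labels say, a reader cannot recover the contrast that the protocol asked for. Cyclosporine, one of the protocol's three options, could not be reported at all.

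**Working it through.** The documents give no event rate, sample size or power for this comparison, so there is no stated figure to reproduce. The check has two parts.

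**1. Set logic, from the text alone.** Take a 6 mg/kg patient on lubricating tears and apply the SAP 7.2 rules.

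| Added by Cycle 1 Day 1 | SAP group |
|---|---|
| Nothing | Lubricating only (correct) |
| Brimonidine | Brimonidine |
| Steroid drops | Steroid |
| Cyclosporine | Lubricating only (label wrong) |
| Agonist other than brimonidine | Lubricating only (label wrong) |
| Brimonidine and steroid drops | Meets both active definitions |

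A patient who starts an active drop after Cycle 1 Day 1 also falls in lubricating only. That is defensible, because the question is primary prophylaxis.

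The steroid group's title implies an eye drop, but its criterion does not say ophthalmic. Read literally, a systemic steroid in the concomitant medication data would qualify.

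**2. Illustrative effect of mislabelling.** All of these inputs are assumptions: a lubricating-only event rate of 40%; a rate of 20% on the studied drop (a true 50% reduction); a share *f* of the labelled control group on another drop; and a risk ratio *r* for that drop against lubricating drops alone.

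Control rate = 0.40 × [(1 − *f*) + *f* × *r*]. Apparent reduction = 1 − 0.20 / control rate.

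With *r* = 0.5:

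- *f* = 10%: control rate 0.38; 1 − 0.20/0.38 = 47.4%.
- *f* = 20%: control rate 0.36; 1 − 0.20/0.36 = 44.4%.
- *f* = 40%: control rate 0.32; 1 − 0.20/0.32 = 37.5%.

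With *r* = 1.0 the control rate stays at 0.40 and the reduction at 50%.

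With *r* = 1.25 (an irritating drop):

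- *f* = 10%: control rate 0.41; reduction 51.2%.
- *f* = 20%: control rate 0.42; reduction 52.4%.
- *f* = 40%: control rate 0.44; reduction 54.5%.

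The sign of the bias therefore depends on *r*, which is unknown.

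**Overlap.** Suppose a share *g* of each active group used both drops and is counted in both.

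- *Brimonidine against steroid.* The difference is 0.40 × (difference in risk ratios) × (1 − *g*). With risk ratios of 0.5 and 1.0, 20 points becomes 15 at *g* = 25% and 10 at *g* = 50%. The contrast shrinks.
- *Active against lubricating.* With risk ratios of 0.5 for each drop and 0.25 for both, the apparent reduction is 1 − [0.5(1 − *g*) + 0.25*g*]. That is 56.25% at *g* = 25% and 62.5% at *g* = 50%. The contrast is inflated.

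**Scale.** Protocol 4.1.3.2 plans sub-study cohorts of 10 to 20, so one patient is 5 to 10 percentage points. At 40% against 20%, a two-sided 5% test would have about 16% power with 10 per group and 28% with 20. No test is planned. These figures only show that imprecision is larger than the effect of moderate contamination.

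**The case against.** The strongest reply is that the defect may be empty in practice. Cyclosporine is used only on instruction, additional drops are optional, and the sub-study is voluntary. Nothing in the documents shows that any 6 mg/kg patient used cyclosporine, another agonist or two active drops. The SAP already names 6 mg/kg and a cycle 1 eye drop compliance form, so its two active groups may simply be the regimens that were deployed. The protocol's advice on spacing multiple drops does not prove combination use, because lubricating tears plus one active drop is already two. The objective is exploratory, and the medication listing in SAP 7.6 should let a reader see other drops recorded as concomitant medication. All of this stands. It limits the consequence but does not make the rule right.

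A reader might infer that the comparison must be biased toward no difference. The documents do not support that. It requires the misplaced drops to be effective, which is what this objective is meant to explore. Protocol 7.2.1 itself says that vasoconstricting and cyclosporine drops may cause ocular symptoms. Overlap can also exaggerate the active-versus-lubricating contrast.

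A reader might also infer that patients will be counted twice, or that a 50% criterion will be missed. The first is an ambiguity in the SAP, not a stated practice. On the second, the protocol offers 50% only as an example. The SAP tables listed for these events cover resolution, time to onset and time to resolution, not a reduction in keratopathy of Grade 2 or higher.

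**Conclusion.** The point holds on the text. The SAP 7.2 groups are not mutually exclusive, and the remainder group is not the lubricating-only comparator of Protocol 4.1.3.2. This conclusion needs no assumption about the data.

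The bias has unknown direction and size. For active against lubricating drops, mislabelling pulls toward no difference only if the misplaced drops work, and could push the other way if they irritate the eye. There is no bias from either source if no such patients exist. The 47%, 44% and 38% are conditional illustrations. They rest on assumed rates of 40% and 20%, an assumed risk ratio of 0.5 for the misplaced drop, and assumed shares of 10%, 20% and 40%.

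The rule should be corrected because it is wrong as written and cheap to change. The documents do not show that a result has been distorted.

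**What to change.** In SAP 7.2:

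- Limit lubricating only to 6 mg/kg patients with no other prophylactic eye drop started on or before Cycle 1 Day 1.
- Make the active groups mutually exclusive: vasoconstrictor, ophthalmic steroid, cyclosporine, and a separate combination group, each with lubricating drops.
- State that steroid means an ophthalmic steroid.
- Report the count in each group. List very small groups instead of comparing them. If the omitted categories are empty, reporting zero settles the point.

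The cost is a few lines of SAP text and one derived variable, which should be obtainable from the concomitant medication and cycle 1 compliance data that the SAP already names. The downside is that some groups become smaller. Classification by assigned regimen is not required: the SAP analysis covers all 6 mg/kg patients, and the data sources it names record use, not assignment.

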9.15.1. Safety

Ongoing TEAEs will be followed until the event has resolved to baseline grade, the event is assessed by the investigator as stable, initiation of another anticancer therapy, withdrawal of consent, LTFU, or death. The investigator should follow and provide updates for all AEs until clinical recovery is complete, laboratory values return to normal, the participant stabilizes, or death occurs to ensure the safety of the participants.

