#### 4.3.1. Missing AE Onset Date

For records with missing AE onset date, the following procedure will be employed for use in determining whether the AE is treatment emergent:

- AE onset dates with missing day and non-missing month will be assumed to occur on the first day of the non-missing month, except for AEs occurring in the first month of dosing, in which case the date will be the first day of dosing.
- AE onset dates with missing month will be assumed to occur on the first day of the non-missing year (ie, January 1), except for AEs occurring in the first year of dosing, in which case the date will be the first day of dosing.

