#### 4.3.4. Missing Death Date

For records with a partial death date, the following procedure will be employed for use in deriving time-to-event variables (eg, PFS).

• The death date will be imputed by the earliest possible date that is not contradicting with any other available data in the database.

All other data will be reported as they are collected. No imputation methods will be used to replace missing data unless otherwise stated in this document.

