# 4.12. Data Display Characteristics

Data displays produced for this study will include summary tables, data listings, and figures. Data listings will be produced for all recorded data as described in Section 5, Section 6, and Section 7. Summary tables will be produced as specified in Section 5, Section 6, and Section 7. Additional data listings will be produced for outcome measures that involve extensive procedures to derive the analyzed outcomes. Figures will be produced when specified in Section 5, Section 6, and Section 7.

Data listings will report the data recorded on the eCRF or derived for each patient. Data will be ordered by patient number, and date/time of assessment. When expedient, additional levels of ordering hierarchy may reflect subsets of assessments within patient. Data listings will not display patient initials.

The summary statistics displayed will be a function of the type of data associated with the summarized assessment. Unless stated otherwise in relevant sections, Section 5, Section 6, and Section 7, continuous data will be summarized with the number of non-missing values, mean, standard deviation, minimum, median, and maximum. Categorical data will be summarized with

the number of non-missing values and the numbers of values equal to each of the possible values. Percentages of patients with each of the possible values will be calculated from the number of patients in the corresponding analysis population, unless stated otherwise. Some continuous variables may also be grouped into categorical levels and evaluated in frequency tables.

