## **6.2.** Efficacy Outcome Analysis

The protocol specifies the following as exploratory analyses:

- To describe antitumor activity of IMGC936 using Response Evaluation Criteria in Solid Tumors version 1.1 (RECIST v1.1)
- To explore progression-free survival (PFS)

The number and percent of participants with their BOR will be presented. The objective response rate (ORR) will be presented together with BOR. Two-sided 95% exact binomial confidence intervals (CIs) of the response rates will be calculated using the method of Clopper—Pearson.

Percent change of tumor size from baseline over time will be summarized and presented by spider plot. The tumor size is defined as the sum of diameters of the target lesions. The best percent change of tumor size from baseline will be presented by waterfall plot.

The Kaplan-Meier method will be applied to estimate PFS and DoR curves; their median times, and PFS rates at 3 and 6 months, respectively. The method of Brookmeyer and Crowley will be used to construct 95% CIs for median time. The 95% CIs for PFS rates at each time point of interest will be calculated by normal approximation after log(-log) transformation.

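### Time to resolution of ocular TEAEs has no stated estimator, so under the SAP default unresolved events fall out of the table and the reported duration is biased short

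*SAP*

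**What the plan says.** SAP 7.2 sets out the aim in one sentence: "Ocular AEs including blurred vision events and grouped keratopathy events will be analyzed for outcome, resolution, time to onset and time to resolution". Its table list then gives titles only: one on ocular TEAE resolution, one on onset ("Time to onset of first ocular TEAE (blurred and keratopathy") and one on duration ("Time to resolution of ocular TEAE (blurred vision and keratopathy"). No method is attached to any of them.

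Four other provisions decide what happens next.

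- **Default summary.** SAP 4.12 says that, unless Sections 5 to 7 state otherwise, "continuous data will be summarized with the number of non-missing values, mean, standard deviation, minimum, median, and maximum".
- **Dates.** The only AE date rule, SAP 4.3.1, concerns onset and exists "for use in determining whether the AE is treatment emergent". SAP 4.3 accepts partial AE resolution dates but gives no rule for completing them. SAP 4.3.4 adds: "No imputation methods will be used to replace missing data unless otherwise stated in this document".
- **Kaplan-Meier.** SAP 6.2 assigns it to two efficacy endpoints: "The Kaplan-Meier method will be applied to estimate PFS and DoR curves". No safety time is included.
- **End of follow-up.** Under Protocol 9.15.1, follow-up of an ongoing TEAE stops at resolution to baseline grade, when the investigator judges it stable, or at "initiation of another anticancer therapy, withdrawal of consent, LTFU, or death". Protocol 7.2 lets repeat eye examinations stop at stabilization. SAP 7.2 describes AE collection as running to 30 days after the last dose, or until the event resolves, stabilizes or returns to baseline.

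**The concern.** A resolution time can be calculated only for an event that resolved. If the table rests on non-missing values, events still open when follow-up ends contribute nothing to it, and long events are the ones most likely to be still open. The reported duration then answers a narrower question than its title suggests: how long the events lasted that were seen to end.

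Resolution time matters in this trial. Protocol 7.2 reports that ocular events have been seen with this drug, and Protocol Table 7 grades its management by how quickly they resolve. A short median would be read as evidence of quick reversibility. SAP 7.2 also plans further analysis of the 6 mg/kg participants by eye-drop group. If this median were compared between those groups, part of any difference could come from unequal follow-up.

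**Working it through.** The plan gives no figure for ocular resolution or onset times, so there is nothing to reproduce. The check has a textual part and an illustrative part.

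**1. Text.** SAP 7.2 names no method, so SAP 4.12 governs. No resolution date is imputed (SAP 4.3.1, 4.3.4), and Kaplan-Meier is not extended to safety times (SAP 6.2). Follow-up may end without resolution (Protocol 7.2 and 9.15.1, SAP 7.2). Applied as written, the plan gives an unresolved event no value and leaves it out.

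**2. Direction.** Let T be the time from onset to resolution and C the follow-up after onset. An event enters the table only if T ≤ C. If C is independent of T, an event of length t enters with probability P(C ≥ t), which falls as t rises. Long events are therefore under-represented and the summary is too short. If every event is followed to resolution, there is no bias.

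**3. One case by formula.** Assume T is exponential with median M, so λ = ln 2 / M, and that follow-up is fixed at C. The share resolved is p = 1 − exp(−λC), and the resolved-only median is −ln(1 − p/2)/λ. With M = 42 and C = 30 days:

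- λ = 0.6931/42 = 0.01650
- p = 1 − exp(−0.495) = 0.390, so 61% are unresolved
- resolved-only median = −ln(1 − 0.195)/0.01650 = 13.2 days, against a true 42

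**4. Range by simulation.** 400,000 events per row; T exponential; C fixed, or uniform over the range shown. Medians and follow-up are assumptions. The shortfall is (true − resolved-only)/true.

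| True median (days) | Follow-up (days) | Unresolved | Resolved-only median | Kaplan-Meier median | Shortfall |
|---|---|---|---|---|---|
| 21 | 30 | 37% | 11.4 | 20.9 | 46% |
| 21 | 30–90 | 16% | 16.5 | 21.0 | 21% |
| 21 | 30–180 | 7% | 18.8 | 20.9 | 10% |
| 42 | 30 | 61% | 13.2 | not reached | 69% |
| 42 | 30–90 | 39% | 22.2 | 42.1 | 47% |
| 42 | 30–180 | 23% | 29.7 | 42.1 | 29% |
| 84 | 30 | 78% | 14.1 | not reached | 83% |
| 84 | 30–90 | 62% | 26.0 | 84.2 | 69% |
| 84 | 30–180 | 45% | 39.5 | 84.2 | 53% |

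Kaplan-Meier recovers the true median, or reports that it was not reached.

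**5. Ten invented events.** Six resolve at days 14, 21, 28, 35, 42 and 60. Four are still open at days 75, 90, 100 and 120. The default gives a median of (28 + 35)/2 = 31.5 days and a mean of 200/6 = 33.3 days. The Kaplan-Meier curve falls to 0.5 at day 42.

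**6. Unequal follow-up.** In the table, two groups with the same true median of 42 days show 22.2 days with 30–90 days of follow-up and 29.7 days with 30–180. The gap of 7.5 days is wholly an effect of follow-up.

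**7. Time to onset.** Here the default leaves out participants without an event. With 84 days of follow-up and exponential onset, λ = −ln(1 − p)/84, where p is the share with an event. The median among those with an event is −ln(1 − p/2)/λ. For p = 30%, 50% and 70% this gives 38, 35 and 30 days, against medians over all participants of 163, 84 and 48 days. Onset looks earlier, and duration is unaffected.

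**The case against.** The strongest reply is that the SAP nowhere says unresolved events are dropped. That is correct: it is an inference from the default, the imputation rule and the limited scope of Kaplan-Meier. It is nevertheless what a programmer following the document would produce, because nothing in SAP 7.2 displaces the default.

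The plan also contains real mitigation. A separate table on ocular TEAE resolution sits just above the two time tables, outcome is to be analyzed, the TEAE listing carries onset and end dates, and the default display shows the number of non-missing values. A careful reader could see that many events stayed open, but the duration figure would remain uncorrected.

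Follow-up may also be better than the shorter scenarios assume. Protocol 9.15.1 asks investigators to follow all AEs until recovery, stabilization or death, and Protocol 7.2 continues eye examinations after the drug is stopped if needed. This could make the bias small. It does not remove it, because stabilization is itself an accepted end without resolution.

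A reader might infer more than the documents support:

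- **That onset and resolution share one fault.** They do not. The onset default makes onset look earlier and says nothing about duration. Onset among affected participants is a legitimate summary if labelled so.
- **That the eye-drop comparison is biased.** SAP 7.2 does not say that these time tables are repeated by eye-drop group. Protocol 4.1.3.2 judges benefit by example criteria on keratopathy of Grade 2 or higher and on ocular AEs leading to dose reduction or discontinuation, not by duration.
- **That ocular events are designated the main toxicity.** Protocol 2.4 lists ocular toxicity among four potential risks, and Protocol 12.2.3 names infusion-related reaction as the only AESI.
- **That the tabulated median is insensitive to the truth.** With 30–180 days of follow-up it moves from 18.8 to 39.5 days as the true median goes from 21 to 84. It is compressed, but it does respond.

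**Conclusion.** The concern holds for time to resolution. Followed as written, the SAP gives a mean and median of resolved events only, and these are too short whenever follow-up cuts off longer events. Both documents foresee follow-up ending without resolution.

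The size cannot be computed from the documents. Under exponential resolution and independent follow-up, the median was about 10% short with 7% unresolved and about 47% short with 39% unresolved; shorter assumed follow-up made it worse. The direction needs only that longer events are more often cut off. The percentages depend wholly on the assumed inputs.

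The planned resolution table lessens the problem without curing it. Any between-group reading of this median would depend on equal follow-up. Time to onset needs only a label or a different denominator. These are descriptive safety summaries, and no hypothesis test depends on them.

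**What to change.** Add to SAP 7.2:

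- **Definition of resolution**, for example the AE end date, or return to Grade 1 or less or to baseline, with a rule for partial end dates.
- **Unit of analysis**, for example the first event per participant, and how recurrences count.
- **Estimator.** Kaplan-Meier for time to resolution, with unresolved events censored at the last ocular assessment.
- **Other endings.** State how events closed as stabilized, deaths and new anticancer therapy are treated: for example as not resolved, or as competing events with cumulative incidence of resolution. Simply censoring stabilized events assumes they could still resolve like the others, which would again shorten the estimate.
- **Display.** Resolved over total events and the number censored, beside the median.
- **Onset.** Label the table as covering participants with an event, or give cumulative incidence over all treated participants.

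The cost is SAP wording and some programming. Onset and end dates are already on the eCRF, and Kaplan-Meier is already used for PFS and DoR. The downside is presentational: resolution times will look longer, and some medians may not be reached.
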